1. SYNOPSIS

Patients with advanced cancer suffer from high symptom burden and aggressive end-of-life care. Early specialty palliative care is an evidence-based practice that improves symptom burden, quality of life, and survival in advanced cancer. However, over half of patients with advanced cancer die before receiving palliative care. Clinician-level biases and suboptimal identification of high-risk patients are major barriers to palliative care uptake. In this 2-arm pragmatic clinical trial, we will randomize practices within a large community oncology network to receive an intervention consisting of algorithm-based default palliative care referrals. We will study the impact of such an intervention on palliative care utilization and end-of-life outcomes.

2. BACKGROUND

2.1 ADVANCED CANCER BURDEN

Over half of patients with advanced cancer report moderate-to-severe symptom burden and poor quality of life – both of which are associated with up to 70% lower overall survival.^{1–3} Despite heavy symptom burden, 40% of patients with advanced cancer receive aggressive end-of-life care, including chemotherapy and lack of hospice referral close to death, that is not concordant with patient goals.⁴ Suboptimal symptom management, poor communication about expected treatment benefit, and lack of attention to patient goals and wishes near the end of life contribute to these gaps.⁵

2.2 PALLIATIVE CARE IMPROVES QUALITY OF LIFE & SYMPTOMS

Palliative care is a medical specialty focused on providing relief from the symptoms and stress of serious illnesses such as cancer and is available in inpatient, outpatient, and community-based settings.⁶ Outpatient palliative care is available at 98% of NCI-designated cancer centers and 63% of non-NCI centers.⁷ Early outpatient palliative care concurrent with cancer-directed treatment improves quality of life, reduces symptom burden, and decreases rates of aggressive end-of-life care.^{8,9} Since 2017, the American Society of Clinical Oncology has recommended specialty outpatient palliative care consultation for patients within 8 weeks of advanced cancer diagnosis.¹⁰ During the COVID-19 pandemic, other organizations have called for earlier palliative care to ensure that high-risk cancer care meets patients' goals.^{11,12} Despite such guidelines, nearly two-thirds of patients with advanced cancer do not receive palliative care prior to death.⁴ Delayed or missed outpatient palliative care referrals are a major contributor to aggressive end-of-life care.⁸

2.3 PALLIATIVE CARE RARELY USED

NCCN-based indications for palliative care referral include limited prognosis and prognostic risk factors, such as uncontrolled symptoms or poor performance status.¹³ Better awareness of mortality risk may inform clinicians' decisions around palliative care referral and prompt goal-concordant cancer care.¹⁴ However, oncologists correctly identify only 20% of patients with advanced cancer who will die in one year and overestimate prognosis for 70% of patients.^{15,16} Furthermore, existing palliative care triggers ignore patient- and cancer-specific heterogeneity in important variables such as laboratories and comorbidities.¹⁷

2.4 IMPROVE SHORT-TERM MORTALITY PREDICTION

Advances in electronic health record (EHR) infrastructure and predictive analytics allow accurate and automated identification of patients with cancer at risk of short-term mortality. We have trained and deployed EHR-based predictive algorithms with better performance (c-statistic >0.80; sensitivity >60%) than traditional prognostic aids into routine oncology practice in order to identify patients who may benefit from early palliative care and advance care planning.^{18,19} At Tennessee Oncology, a rules-based automated EHR algorithm based on 14 components derived from 2021 NCCN guidelines (**Exhibit 1**) accurately identifies patients at risk of 180-day-month mortality.²⁰ This algorithm has been incorporated in pilot studies, and has generated weekly reports of high-risk patients who may benefit from timely palliative care referral.

There is an urgent need to implement strategies based on algorithm-based triggers to increase early outpatient palliative care among patients with advanced cancer.

2.5 PALLIATIVE CARE UNDERUTILIZED

Two-thirds of patients with advanced cancer do not receive palliative care prior to dying. Furthermore, clinicians underutilize palliative care, usually initiating referrals only 2 months before death. Lack of standardized referral and screening criteria for outpatient palliative care contributes to underutilization. This is particularly true for Black and Hispanic populations, for whom palliative care referrals are 50% lower compared to White populations.

2.6 PALLIATIVE CARE BIASES

Status quo bias, which predisposes clinicians to continue current practice even if not the optimal option, may lead to delayed or missed palliative care referrals. Additionally, *optimism bias*, the cognitive bias that causes clinicians to believe that their own patients are at lesser risk of negative outcomes, may cause clinicians to underestimate a patient's mortality risk, thus delaying palliative care referral. Finally, *overconfidence bias*, the propensity to overestimate one's desired behaviors when it is not objectively reasonable, may lead clinicians to incorrectly believe they are initiating similar or more palliative care referrals than their peers.

2.7 PALLIATIVE CARE CONSTRAINTS

Despite increasing availability in tertiary cancer care settings, specialty palliative care is sparsely available in community oncology practices – where 75% of patients receive their primary oncologic care. Furthermore, while the number of patients with cancer eligible for palliative care is expected to grow by 20% in the upcoming decade, there will be a shortage of 18,000 palliative care specialty physicians, particularly in the outpatient setting. Because of these capacity constraints, it is crucial to identify scalable strategies to automatically identify high-risk patients with advanced cancer in order to initiate timely outpatient palliative care referrals.

2.8 PALLIATIVE CARE UTILIZATION IMPROVEMENTS

Overcoming suboptimal clinician decision-making biases is key to increasing palliative care referrals. Principles from behavioral economics can inform “nudges” that change how clinicians receive information and make choices such as palliative care referral. Default, opt-out nudges that make the optimal choice the path of least resistance can mitigate clinicians’ status quo bias. Reframing clinicians’ prognoses via “triggered” identification of high-risk patients may combat optimism bias. Finally, peer comparisons use social comparisons to counter overconfidence bias in order to increase guideline-based practice. These strategies are associated with 10-25 absolute percentage-point increases in guideline-based practices such as statin prescribing and transition from brand to generic drugs. However, to our knowledge no published randomized trials have used behavioral strategies to improve palliative care utilization in advanced cancer.

Given rising demand for palliative care with constrained supply across the United States oncology care system, our contribution will be significant because it will leverage scalable automated predictive algorithms with a behaviorally informed intervention to increase palliative care utilization among high-risk patients with advanced cancer. This intervention is expected to create a feasible, adaptable, and acceptable process in a community oncology setting that increases palliative care utilization earlier in the advanced cancer disease trajectory.

3. **OBJECTIVES & OUTCOMES**

3.1 OVERALL OBJECTIVES

Our main objective is to evaluate the impact of an intervention consisting of default algorithm-based referrals, compared to usual practice, on outpatient palliative care visits and quality of end-of-life care among patients with advanced cancer. We hypothesize that this intervention will increase palliative care visits by 10 percentage points and decrease aggressive end-of-life utilization by 15 percentage points, relative to usual practice.

We will also explore physician and practice-related facilitators and barriers to completion via mixed-methods interviews. After completing initial enrollment, we aim to conduct a qualitative study through approximately 20 semi-structured interviews with:

1. medical oncology clinicians in the intervention group to understand the impact of the risk-algorithm and behavioral nudges on their workflow, and explore barriers and facilitators for feasibility, scalability, and ultimately increasing palliative care referrals for patients with advanced lung or non-colorectal gastrointestinal malignancies.
2. palliative care clinicians who saw patients referred through the study to explore their perspectives on seeing patients identified by the risk-algorithm and default referrals.

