3.2 PRIMARY OUTCOME

Completed palliative care visit within 3 months among high-risk patients with stage III and IV lung and non-colorectal GI malignancies

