3.3 SECONDARY OUTCOMES

- Completed palliative care visit among non-high risk patients with stage III and IV lung and non-colorectal GI malignancies.

We will also assess on an exploratory basis the impact on acute care utilization including emergency room visits and hospitalizations within participating hospitals in the state of Tennessee; completed palliative care visits among all patients at Tennessee Oncology, number of opioid prescriptions, aggressive end-of-life care (no hospice referral or enrollment prior to death, hospice enrollment<3 days before death, location of death and/or chemotherapy receipt within 14 days of death); and patient-reported measures such as depression and pain. We will also assess on an exploratory basis the quality of life of patients in the intervention group and control group through the FACIT-PAL 14, and “Heard & Understood” instrument before the palliative care visit, and after the visit at 1-month, 3-month and 6-month intervals (see **Exhibit 4**).

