6.4 ANALYSIS MEASURES

The primary study endpoint is completion of a palliative care visit within 3 months of enrollment *among high-risk patients*. The secondary outcome is completion of palliative care visits among non-high-risk patients.

We will also assess on an exploratory basis the impact on acute care utilization including emergency room visits and hospitalizations within participating hospitals in the state of Tennessee; completed palliative care visits among all patients at Tennessee Oncology; number of opioid prescriptions; aggressive end-of-life care (no hospice referral or enrollment prior to death, hospice enrollment<3 days before death, location of death and/or chemotherapy receipt within 14 days of death) and patient-reported measures including depression, pain, quality of life measured by FACIT-PAL 14, and the heard and understood measure. All exploratory outcomes will be measured by descriptive statistics.

Patients will be followed for exploratory outcomes for six months or death.

The semi-structured interviews will be transcribed and uploaded to Atlas.ti, a data management software. We will inductively develop a codebook following the initial interviews based on the structure of the interview guide. One of two reviewers will code each transcript, and approximately 20-

25% of total transcripts will be coded by both reviewers to establish inter-rater reliability. The adequacy of the codebook will be periodically assessed by the reviewers in partnership with the research team and modifications will be made as their understanding of the data and emergent themes evolves over time. The reviewers will meet regularly to discuss discrepancies and update the code book as needed, with record keeping adequate to track changes to the code book and the rationale. Kappa statistics will be generated to estimate inter-rater reliability. Coding will then be reviewed to summarize key themes, and representative quotes will be selected to illustrate those themes.

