6.5 SAMPLE SIZE

Currently, there are approximately 4000 eligible patient-encounters over a six-month period at our study practices. Given prior work showing the algorithm flags 8-10% of eligible patients as high-risk, we anticipate enrolling at least 360 patients. The unit of analysis is the patient. We will use multilevel mixed-effects models, adjusted for relevant covariates, to assess outcomes. Assuming baseline palliative care rate=26.9% (SD=10%), a 10% dropout rate, two-sided alpha=0.05, a sample of 360 patients (180 intervention, 180 control) will provide 80% power to detect a meaningful 15 percentage-point increase in palliative care visits.

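### Section 3.1 hypothesises a 10-point rise in palliative care visits while section 6.5 sizes the trial for 15 points, without explanation; power for 10 points is about 49-53% before clustering

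*Combined protocol and SAP*

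**What the plan says.** Section 3.1 sets the objective as the effect of default referrals "on outpatient palliative care visits and quality of end-of-life care among patients with advanced cancer". It then gives two hypothesised effects in one sentence: a rise of 10 percentage points in visits ("We hypothesize that this intervention will increase palliative care visits by 10 percentage points") and a fall of 15 percentage points in aggressive end-of-life utilization.

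Section 3.2 limits the primary outcome to one group: "Completed palliative care visit within 3 months among high-risk patients". Section 6.4 agrees: "The primary study endpoint is completion of a palliative care visit within 3 months of enrollment", again in high-risk patients. Visits in other groups are listed separately in section 3.3, as the secondary outcome ("Completed palliative care visit among non-high risk patients with stage III and IV lung and non-colorectal GI malignancies") and as an exploratory one ("completed palliative care visits among all patients at Tennessee Oncology").

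Section 6.5 gives the inputs for the sample size: "Assuming baseline palliative care rate=26.9% (SD=10%), a 10% dropout rate, two-sided alpha=0.05". With 180 patients per arm, it says the sample "will provide 80% power to detect a meaningful 15 percentage-point increase in palliative care visits". It derives the expected enrolment from about 4000 eligible encounters and a high-risk flag rate of 8-10%, and presents 360 as a minimum. Sections 4.1 and 4.4 give a target of about 400.

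Section 2.8 reports that behavioural strategies raised other guideline-based practices by 10-25 points. That range holds both figures and does not choose between them.

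**The concern.** The hypothesised effect and the effect used for the sample size are usually the same number, or the plan says why they differ. Here they differ in the unfavourable direction: the authors state that they expect 10 points and size the trial for 15. Section 6.5 also calls the 15-point rise meaningful, which leaves open whether the hypothesised 10 points would count as meaningful.

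What is at stake is how the primary result will be read. If 10 points is the true effect in high-risk patients, the trial has roughly even odds of missing it. A small positive, non-significant result might then be reported as evidence against the hypothesis when it is compatible with it. If 15 points was intended throughout, section 3.1 misstates the hypothesis.

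**Working it through.** **Inputs.** From section 6.5: control rate p0 = 0.269, two-sided alpha 0.05, 10% dropout, equal arms, 360 enrolled. From sections 4.1 and 4.4: about 400 enrolled. Section 6.5 does not say what its SD of 10% describes. It is not needed for a comparison of two proportions and is not used here. The documents give no intracluster correlation, so the main figures ignore clustering.

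**Evaluable patients per arm**, n = enrolled x 0.9 / 2:
- 360 gives 162
- 400 gives 180
- 320 gives 144

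**Power formula** (normal approximation, pooled variance under the null):

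power = Phi[(d - 1.96 x SE0) / SE1], where SE0 = sqrt(2 x pbar x (1 - pbar) / n), SE1 = sqrt((p0(1 - p0) + p1(1 - p1)) / n), p1 = p0 + d and pbar = (p0 + p1) / 2.

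**Step 1: the plan's own figure, 15 points (26.9% to 41.9%).** At n = 162, pbar = 0.344, SE0 = 0.0528 and SE1 = 0.0521. Power = Phi[(0.15 - 0.1035) / 0.0521] = Phi(0.893) = 81.4%. In reverse, 80% power needs 157 evaluable per arm, or 175 per arm after dropout and 350 in total, against the stated 360. The section 6.5 claim reproduces.

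**Step 2: the section 3.1 effect, 10 points (26.9% to 36.9%), same inputs.** At n = 162, pbar = 0.319, SE0 = 0.0518 and SE1 = 0.0515. Power = Phi[(0.10 - 0.1015) / 0.0515] = Phi(-0.029) = 48.8%.

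| Enrolled | Evaluable per arm | Power, 10 points | Power, 15 points |
|---|---|---|---|
| 360 | 162 | 48.8% | 81.4% |
| 400 | 180 | 53.0% | 85.3% |

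**Step 3: size needed for 80% power at 10 points.** n = [1.96 x sqrt(2 x 0.319 x 0.681) + 0.842 x sqrt(0.269 x 0.731 + 0.369 x 0.631)]^2 / 0.10^2 = (1.292 + 0.552)^2 / 0.01, which rounds up to 340 evaluable per arm. Then 340 / 0.9 rounds up to 378 per arm, or 756 in total.

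**Step 4: what a non-significant result would show at 360 enrolled.** The 95% half-width is 1.96 x sqrt((p0(1 - p0) + p1(1 - p1)) / 162).
- Observed rise of 5 points: half-width 9.9 points, interval -4.9 to 14.9. This contains both 0 and 10.
- Observed rise of 0: half-width 9.7 points, interval -9.7 to 9.7. This just excludes 10.

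**Step 5: clustering, as a range only.** Assume 17 equal practices, 324 evaluable patients (19.06 per practice) and an intracluster correlation of 0.01 to 0.05. These correlations are assumptions and are not in the documents. The design effect is 1 + 18.06 x 0.01 = 1.18 up to 1 + 18.06 x 0.05 = 1.90. Power for 10 points falls to about 43% down to 29%, and for 15 points to about 75% down to 54%.

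**Step 6: the enrolment figure.** 0.08 x 4000 = 320 and 0.10 x 4000 = 400, so 360 is the midpoint of the plan's own range. At 320 enrolled (144 evaluable per arm), power for 15 points is Phi(0.729) = 76.7% before clustering.

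**The case against.** A hypothesised effect and a design effect may legitimately differ, and section 6.5 is clear about its own. A reader might infer from the mismatch that the plan does not say which effect the trial was sized to detect. The documents do not support that: 6.5 is the only place that states power, and it names 15 points. Nor does the plan claim 80% power for 10 points anywhere. What stands is narrower: the gap between the two figures is unexplained, and the stated hypothesis is the one with weak power.

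The two figures might concern different populations. Section 3.1 speaks of patients with advanced cancer, whereas the primary outcome covers high-risk patients. A reader might infer that 3.1 means all eligible patients. No passage says so, and section 4.4 describes the roughly 400 trial patients in similarly general terms, so the wording of 3.1 can equally mean the enrolled cohort. This reading remains open, and under it the plan would state no hypothesis for the primary population.

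The simplest explanation is a slip. The sentence in 3.1 pairs 10 points with visits and 15 points with end-of-life care, so a figure may have been transposed or carried over. The documents cannot settle this, but if it is right, one line corrects it.

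A reader might also infer that any null result would be uninformative about 10 points. That goes too far, as Step 4 shows: an observed difference near zero would exclude 10 points, though narrowly and before clustering.

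On enrolment, 320 is not a hard lower limit. Section 6.1 allows enrolment to be spread over three years by amendment. The same sentence, however, also contemplates a higher risk threshold, which would reduce the number flagged.

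**Conclusion.** The concern holds as an unexplained inconsistency between sections 3.1 and 6.5. It is not a miscalculation. With 360 to 400 enrolled, the design has about 49-53% power for the effect that 3.1 hypothesises, against 81-85% for the effect in 6.5. About 756 enrolled would be needed for 80% power at 10 points, roughly twice the plan. These figures rest on the 26.9% control rate, two-sided 0.05 and 10% dropout of section 6.5, and on treating patients as independent. Because practices are randomised, they are upper bounds with respect to clustering. The practical consequence is limited to small positive, non-significant results, which could not rule out the hypothesised effect. The endpoint and the analysis model are not affected. It should be corrected. The presentation of 360 as a minimum is a lesser error in the same section.

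**What to change.** State one effect for the primary outcome, in high-risk patients, in both 3.1 and 6.5. The authors know which of these applies:

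1. If 15 points is the hypothesis, correct 3.1.
2. If 10 points is the expected effect, keep it in 3.1. State in 6.5 that power for it is at most about 49-53% before clustering, and describe 15 points as the effect the size was planned around.
3. If 3.1 refers to another population, name that population and state the high-risk hypothesis separately.

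As a minor change, replace the floor of 360 in 6.5 with about 320-400, and give power at the lower end (about 77% for 15 points at 320, before clustering).

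The cost is wording in two sections. The downside is that the stated power becomes less favourable; under the second option the plan must print power of about one half for its own hypothesis. No change to the design or sample size is required.

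### A 15-point fall in aggressive end-of-life care is part of the main hypothesis, but the outcome is exploratory, descriptive only, not allowed for in the sample size and lacks a denominator

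*Combined protocol and SAP*

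**What the plan says.** Section 3.1 sets the main objective as the effect "on outpatient palliative care visits and quality of end-of-life care among patients with advanced cancer". It attaches a number to each half: a 10-point rise in palliative care visits, and that the intervention will "decrease aggressive end-of-life utilization by 15 percentage points".

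Section 3.3 introduces a list of further outcomes, aggressive end-of-life care among them, with "We will also assess on an exploratory basis the impact on acute care utilization". Section 6.4 repeats the list and adds: "All exploratory outcomes will be measured by descriptive statistics". These outcomes are followed for six months or until death.

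The items that make up aggressive end-of-life care are given in brackets in 3.3 and 6.4: "no hospice referral or enrollment prior to death, hospice enrollment<3 days before death", then "location of death and/or chemotherapy receipt within 14 days of death".

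Section 6.5 contains the only model statement: "We will use multilevel mixed-effects models, adjusted for relevant covariates, to assess outcomes". It then justifies 360 patients (180 per arm) by 80% power for a 15-point increase in visits from a 26.9% baseline. It gives no control rate, number of deaths, power or precision for end-of-life care.

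**The concern.** A numeric claim in the main hypothesis should have an estimate, a measure of uncertainty and a defined outcome behind it. Here the objective and the analysis section treat the same outcome at different levels. Practices are randomised, at most 17 of them, so a raw difference between arm percentages says little without an interval that reflects practice. Such a difference would nevertheless sit beside a published expectation of 15 points.

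Two further gaps matter once a single figure is to be compared with 15 points. Nothing says whether the percentage is of enrolled patients or of patients who die. Nothing says whether the bracketed items are combined, and if so by what rule. If both are left open until the data are in, the choice can follow the result.

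**Working it through.** **Setting the sections side by side.** Section 3.1 puts the outcome in the main hypothesis. Sections 3.3 and 6.4 put it among the exploratory outcomes. Section 6.4 is explicit and covers all exploratory outcomes. Section 6.5 speaks of outcomes in general and names none. The specific sentence probably governs. If the model was meant to apply here, the two sections conflict. Either way, no cluster-adjusted interval is clearly planned for this outcome.

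**Reproducing the plan's own figure.** Inputs from 6.5: 26.9% versus 41.9%, two-sided alpha 0.05, 180 per arm less 10% dropout = 162 per arm.

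Power = Φ[(d − 1.96·se0)/se1], where se0 uses the pooled proportion and se1 the separate proportions.

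- se0 = √(0.344 × 0.656 × 2/162) = 0.0528
- se1 = √[(0.269 × 0.731 + 0.419 × 0.581)/162] = 0.0521
- Power = Φ[(0.15 − 0.1035)/0.0521] = 81.4%

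This agrees with the stated 80%, for visits and with patients treated as independent. The 15 points in 6.5 are therefore a rise in visits. They do not provide power for the 15-point fall in 3.1, although the number is the same.

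**Illustration for end-of-life care.** Assumptions, none of them given for this trial:

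- Denominator: patients who die within six months, because every listed item refers to death.
- Control rate 40%. This is the background figure in section 2.1 for advanced cancer generally. It is described there by chemotherapy and lack of hospice referral near death, which is not the list in 6.4.
- Intervention rate 40 − 15 = 25%.
- 30 to 60% of 360 patients die, split equally by arm.

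For 54 deaths per arm, se0 = √(0.325 × 0.675 × 2/54) = 0.0901 and se1 = √[(0.24 + 0.1875)/54] = 0.0890. Power = Φ[(0.15 − 0.1767)/0.0890] = 38%. The CI half-width is 1.96 × 0.0890 = 17 points. The last two columns apply a design effect of 1 + (m − 1) × 0.02, where m is total deaths divided by 17 and 0.02 is an assumed practice-level ICC.

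| Share dying | Deaths per arm | Power | 95% CI half-width | Power, ICC 0.02 | Half-width, ICC 0.02 |
|---|---|---|---|---|---|
| 30% | 54 | 38% | 17 points | 35% | 18 points |
| 40% | 72 | 48% | 15 points | 43% | 16 points |
| 50% | 90 | 58% | 14 points | 50% | 15 points |
| 60% | 108 | 65% | 12 points | 56% | 14 points |

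For 80% power the same formula needs 152 deaths per arm, 304 in total, before any allowance for clustering. That is 304/360 = 84% of patients dying within six months, or 304/400 = 76% with the approximately 400 patients named in 4.1.

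**Effect of the denominator.** If the same share dies in each arm, a 15-point difference among deaths becomes 0.30 × 15 = 4.5 to 0.60 × 15 = 9 points per enrolled patient. The 15-point hypothesis therefore means different things under the two denominators.

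**The case against.** The strongest reply is that the outcome is openly exploratory. No decision rule or sample size depends on it, and the primary outcome is consistently a completed visit. Low power is a weak criticism of something the plan does not propose to test. Section 6.5 can be read as extending the mixed models to all outcomes, and descriptive statistics do not rule out an interval. The illustrative inputs are borrowed. Neither 3.3 nor 6.4 confines this outcome to high-risk patients, so even the 360 is an assumption here. A wider population would change the number of deaths, though it would also dilute any effect.

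Much of this stands. Exploratory status is legitimate, and the power range shows only an order of size. What the reply does not remove is the mismatch: the numeric hypothesis is in 3.1, and no section clearly plans an estimate with an interval for it.

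A reader might go further in three ways that the documents do not support.

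- That the plan analyses this outcome among decedents. No denominator is written. Deaths are an inference from how the items are defined.
- That the outcome cannot be scored because no location of death is marked as aggressive. The documents never call the list a composite. If the items are tabulated separately, location needs no direction. A rule is needed only for a single figure.
- That better survival would distort the group of patients who die. The synopsis says early palliative care "improves symptom burden, quality of life, and survival in advanced cancer", but that concerns receiving the care. The arms are expected to differ by only 10 points (3.1) or 15 points (6.5) in visits, so any difference in six-month deaths would be diluted, and the documents give no size for it.

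**Conclusion.** The concern holds as an inconsistency between objective and analysis. One half of the main hypothesis has a number but no clearly planned cluster-adjusted estimate, no sample-size basis, no stated denominator and no combination rule. As written, the trial could not properly assess it.

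It would go too far to say that the hypothesis can never be addressed. A descriptive difference can be reported once the outcome is defined, and an interval can be added with data already being collected.

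Under the stated assumptions, the 95% CI half-width of about 12 to 17 points is close to the hypothesised effect itself, and power is about 38 to 65%. Both are worse with clustering. These figures depend on an assumed share dying, a background control rate with a different definition and, in the clustered columns, an assumed ICC. The mismatch between sections depends on none of them. The point should be corrected, but it does not touch the primary analysis.

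**What to change.** - **Section 3.1:** label the end-of-life hypothesis exploratory, or drop the 15-point figure.
- **Section 6.4:** replace descriptive-only reporting of this outcome with an arm difference and 95% CI from a model that accounts for practice, the randomised unit. Make no significance claim.
- **Section 6.5:** say which outcomes the mixed-model sentence covers, so that it agrees with 6.4.
- **Denominator, in 3.3 and 6.4:** use deaths within six months as the main one. Give the per-enrolled proportion as a supporting figure only, because it counts every survivor as free of aggressive care and so mixes mortality with quality of care.
- **Scoring, in 3.3 and 6.4:** say whether the items are combined, and by what rule, or tabulated separately. Report location of death separately unless the locations that count are named.
- **Timing:** fix the denominator and scoring before arm-level data are seen.

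The cost is a more modest stated aim, some wording and a little extra analysis, with no new patients or data collection. With at most 17 practices and possibly few deaths in each, the mixed model may not fit well. A simpler cluster-robust or practice-level summary method should be named as the fallback.
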